8.1 Potential for Benefits

There may not be any direct benefit. However, participants taking part in this pilot may benefit from exposure to information about cancer and HIV with which they were previously unfamiliar. They may also get exposed to basic cognitive-behavioral stress management techniques while reviewing the web-based platform. As mentioned earlier, our culturally-tailored SmartManage platform will be specifically designed to ameliorate the distress, general stress, and health-related quality of life challenges experienced among HIV+ sexual minority male cancer patients. Thus, participants may absorb information about ways to decrease distress, cope with challenges related to symptom management, and improve their HRQoL, all through exposure to an innovative new online tool.

9 UNANTICIPATED PROBLEMS

9.0 Definition of Unanticipated Problems

The Office for Human Research Protections (OHRP) considers unanticipated problems Confidential

involving risks to participants or others to include, in general, any incident, experience, or outcome that meets all of the following criteria:

- Unexpected in terms of nature, severity, or frequency given (a) the research procedures that are described in the protocol-related documents, such as the Institutional Review Board (IRB)-approved research protocol and informed consent document; and (b) the characteristics of the participant population being studied;
- Related or possibly related to participation in the research (“possibly related” means there is a reasonable possibility that the incident, experience, or outcome may have been caused by the procedures involved in the research); and
- Suggests that the research places participants or others at a greater risk of harm (including physical, psychological, economic, or social harm) than was previously known or recognized.

9.1 Unanticipated Problem Reporting

The investigator will report unanticipated problems (UPs) to the reviewing Institutional Review Board (IRB) as per institutional guidelines.

9.2 Reporting Unanticipated Problems to Participants

Not Applicable

10 DATA REPORTING

10.0 Data submission

Electronic case report forms for study data entry will be developed by staff at the University of Miami using Velos and REDCap, a HIPAA AND 21 CFR part 11 compliant database. Only investigators and assigned research staff will have access to study data. The electronic case report forms will be available to the sponsor, IRB or regulatory authorities in event of an audit

10.1 Data and Safety Monitoring

The Sylvester Comprehensive Cancer Center (SCCC) Data and Safety Monitoring Committee (DSMC) will monitor this clinical trial according to the Cancer Center’s data and safety monitoring (DSM) plan to assure the well-being of patients enrolled on Investigator-Initiated Trials that do not have an outside monitoring review. In its oversight capacity, the DSMC bears responsibility for suspending or terminating this study. The activities of this committee include ongoing review of accrual, periodic review of response adverse events including SAEs, important medical events, significant revisions or amendments to the protocol, and approval of cohort/dose escalations. The DSMC also reviews reports from internal audits of protocol compliance and data integrity conducted by the University of Miami, Office of Research Compliance Assessment. If the DSMC and/or the PI have concerns about unexpected safety issues, the study will be stopped and will not resume until the issues are resolved. The DSMC will review reports from all audits, site visits, or study reviews pertaining to this clinical trial and take appropriate action. The guidelines appearing in this section are offered for DSMC consideration in assessing adverse events and response to study treatment. The SCCC DSM Plan to which this study is subject can also be found at www.sylvester.org.

11 STATISTICAL METHODS

11.0 Statistical Hypothesis

Primary research question: To examine the feasibility and acceptability of the culturally-tailored web-based SmartManage intervention among dually-diagnosed Latino SMM.

Primary Hypothesis: The culturally-tailored web-based SmartManage intervention will be feasible and acceptable to dually-diagnosed Latino SMM.

Secondary research question: To evaluate the preliminary efficacy of the culturally-tailored, web-based SmartManage intervention among dually-diagnosed Latino SMM.

Secondary Hypothesis: The culturally-tailored web-based SmartManage will show preliminary reductions in stress and disease-related distress and improvements quality of life among dually-diagnosed Latino SMM.

11.1 Sample Size Determination

We expect that, within this subgroup of HIV+ sexual minority men, rates of prevalence of cancer will likely be greater or equal to 30% (i.e. the rate of prevalence observed in the general older male population). This estimate, along with consultations with our co-investigators and community partners has informed our recruitment goals. Based on our institution accrual capacity, we are able to enroll 30 subjects in the study. In accordance with Leon et al. 2011,²⁹ we assert that the main goal of our pilot study is to examine the feasibility and acceptability of a culturally-tailored SmartManage intervention and based our sample size on the number of participants that could feasibly be recruited within our time frame. Thirty participants will be assessed for retention and attendance rates. As detailed here, 30 participants provide reasonable precision for estimating the above rates. Table 1 illustrates study precision for estimating the true attendance rate. If we observe 21 participants among 30 who attend all intervention sessions, the estimated attendance rate will be 70% and the corresponding 95% confidence interval will be 50.6% to 85.3%. If the number of participants who attend all intervention sessions is 27, then the estimated attendance rate will be 90% with a corresponding 95% confidence interval of 73.5% and 97.9%. Furthermore, with 30 participants, a one-sided binomial test with 5% significance will have power >80% to detect improvement to 18.6% attendance relative to a null rate of 70%.

Table 1. Possible study findings for attendance rate with 30 subjects

Number (%) of attended subjects	95% CI*
21 (70%)	50.6% - 85.3%
24 (80%)	61.4% - 92.3%
27 (90%)	73.5% - 97.9%

* CI: confidence interval, binomial method.

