11.2 Statistical Analyses

11.2.1 General Approach

All data will be inspected for quality assurance prior to analysis. Data screening will focus on: (a) Missing data: we will determine the amount, the pattern, and randomness; (b) Outliers: we will identify observations that appear to be very high or very low and decide how to proceed based on the presumed cause; and (c) Inconsistencies: we will identify inconsistencies within a single variable and between variables. Initially, we will perform an exploratory data analysis and calculate descriptive statistics.

Transformations of the data in order to meet statistical assumptions will be undertaken when indicated. Type-1 error will be set to 5% ($\alpha = .05$) for calculating confidence intervals and performing hypothesis testing and all tests will be two-sided. If needed,

alphas will be adjusted accordingly for multiple comparisons using Bonferroni correction. Standard statistical goodness-of-fit measures will be used assessing any of the model fittings. Missing values will be handled with appropriate statistical methods. Last observation carried forward (LOCF) and multiple imputation will be considered for missing values.

Demographic and disease characteristic variables will be summarized using descriptive statistics. Counts and percentages will be used to summarize the distribution of categorical variables. Median, range, mean, and standard deviation will be used for continuous variables. Categorical variables will be tested using Fisher's exact test. Continuous variables will be tested using Student's t-test and/or Mann-Whitney U test. For correlation coefficients, Pearson's correlation coefficients and Spearman's correlation coefficients will be estimated along with corresponding 95% confidence interval. All statistical analyses will be carried out using SAS or SPSS, all of which are available to investigators through the University of Miami.

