11.2.2 Analysis of the Primary Endpoint(s)

Feasibility will be analyzed using attendance and retention rates. For the proposed study to be considered feasible, we will need to uphold all the following criteria: 70% of participants attend all intervention sessions and 85% of participants are retained throughout the study (from pre-intervention to post-intervention assessment). These proportions are based on previously successful CBSM trials in other populations.

We will also perform descriptive analyses to better understand the feasibility of our future R01 trial, including:

- 1) Personnel time: This will include personnel time that is devoted to assessing eligibility, managing contacts, and recruiting, conducting the intervention, and administrative time.
- 2) Space: We will collect information on any space used that is needed to conduct the intervention, including administrative space.
- 3) Supplies: We will collect information on all supplies that are needed and any costs associated with maintaining the SmartManage website.

Acceptability will be analyzed using the proportion of the number of participants who agree to participate in the intervention. We will evaluate the acceptability of the intervention two ways:

1) via the proportion of eligible SMM who agree to participate vs. decline and 2) via the exit survey that will measure acceptability of the intervention.

We will explore whether feasibility and acceptability differ by sociodemographic, medical, and psychosocial factors via Fisher's exact tests. These analyses will be primarily descriptive and will provide the basis for future randomized trials to formally evaluate the efficacy of the culturally-tailored web-based SmartManage intervention among dually-diagnosed Latino SMM.

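### The power sentence in section 11.1 cannot stand: it uses a one-sided test where section 11.2.1 makes all tests two-sided, and its alternative of 18.6% lies below the 70% null

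*Combined protocol and SAP*

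**What the plan says.** Section 11.1 (Sample Size Determination) gives two kinds of statistical support for 30 participants. The first is precision: Table 1 lists 95% intervals for 21, 24 and 27 attenders, with the footnote "CI: confidence interval, binomial method". The second is a single power sentence, according to which "with 30 participants, a one-sided binomial test with 5% significance will have power >80" per cent. The same sentence gives the effect as "power >80% to detect improvement to 18.6% attendance relative to a null rate of 70" per cent.

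Section 11.2.1 (General Approach) sets the rule for the whole analysis. It says "Type-1 error will be set to 5" per cent for confidence intervals and for "performing hypothesis testing and all tests will be two-sided". It makes no exception for attendance, and 11.1 does not say that it departs from the general rule.

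Two further statements limit what follows. Section 11.1 says that the team "based our sample size on the number of participants that could feasibly be recruited within our time frame". Section 11.2.2 defines feasibility by the criteria that "70% of participants attend all intervention sessions and 85% of participants are retained throughout the study", and names no binomial test.

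**The concern.** A one-sided 5% test and a two-sided 5% test cannot both govern the same attendance comparison. With 30 participants the count is coarse, so one step in the critical value changes power by 15 to 20 percentage points. The printed alternative is a separate fault in the same sentence: a rate of 18.6% is not an improvement on 70%, so a reader cannot tell which true rate the stated power refers to.

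This is the only power figure in the plan, and it concerns a primary feasibility endpoint. If a test against 70% is reported alongside the descriptive result, significance at 26 of 30 could depend on a choice of sidedness and method made after the data are seen.

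**Working it through.** **Inputs.** n = 30, null rate 70%, one-sided 5% and stated power above 80% (section 11.1); two-sided 5% (section 11.2.1). The intended alternative is not usable as printed. Two values are assumed to show a range: 88.6% (70% plus 18.6 points) and 90% (the highest row of Table 1).

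**Formula.** For X ~ Binomial(30, p), the upper tail at count c is P(X ≥ c | p) = Σ C(30,k) p^k (1−p)^(30−k), summed over k = c to 30. At p = 0.70 this is the size of the rule; at the true rate it is the power.

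**Step 1: the plan's own figures.** The three intervals in Table 1 reproduce with the exact (Clopper-Pearson) method: 50.6–85.3%, 61.4–92.3% and 73.5–97.9%. The power figure does not reproduce with the exact test at 88.6%. Large-sample one-sided formulas at 88.6% come near it:

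- normal: Φ[(0.186 − 1.645 × √(0.70 × 0.30/30)) / √(0.886 × 0.114/30)] = Φ[(0.186 − 1.645 × 0.0837)/0.0580] = 79.8%
- normal with continuity correction: 70.8%
- arcsine: 82.4%

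Taken literally, at a true rate of 18.6%, there is no power to show an improvement.

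**Step 2: critical counts under the 70% null.**

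- P(X ≥ 25) = 0.0766
- P(X ≥ 26) = 0.0302
- P(X ≥ 27) = 0.0093

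One-sided 5%: 0.0766 is too large and 0.0302 qualifies, so the rule rejects at 26 or more, with actual size 3.0%. Equal-tailed two-sided 5% (2.5% in the upper tail): 0.0302 is too large and 0.0093 qualifies, so the rule rejects at 27 or more.

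**Step 3: power.**

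| Rule | True rate 88.6% | True rate 90% | Rate for 80% power |
|---|---|---|---|
| One-sided, ≥26/30 | 74.7% | 82.5% | 89.53%, so about 89.6% |
| Two-sided equal-tailed, ≥27/30 | 54.9% | 64.7% | 92.25%, so about 92.3% |

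The last column needs no assumed alternative. It is rounded up because at 89.5% and 92.2% power is still just short, at 79.8% and 79.7%.

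**Step 4: dependence on the two-sided method.** At 26 of 30:

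- Doubling the tail: 2 × 0.0302 = 0.060, not significant.
- Minimum likelihood: P(X ≥ 26) + P(X ≤ 15) = 0.0302 + 0.0169 = 0.047, significant.
- Uncorrected z-test: (26/30 − 0.70)/0.0837 = 1.99, significant.

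Under the last two methods the critical count stays at 26, and power is as in the first row of the table.

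**Step 5: which method fits the rest of the plan.** The exact intervals of Table 1 put 2.5% in each tail. The same method at 26 of 30 gives 69.3% to 96.2%, which includes 70%. So at 26 of 30 the interval method and the one-sided test in the same section disagree. At 27 of 30 the lower limit is 73.5% and they agree.

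**The case against.** The strongest reply is that little depends on this sentence. Section 11.1 bases the sample size on how many participants can be recruited and offers the power statement only as an addition to the precision argument. Section 11.2.2 judges feasibility on observed proportions, and the Protocol Summary calls the analyses primarily descriptive. Under those criteria 26 of 30 (86.7%) passes on attendance whichever sidedness applies. This stands, and it limits the consequence.

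A reader might infer that the two-sided rule is what brings power below 80%. The documents do not support that. If 88.6% was intended, the exact one-sided test already gives only 74.7%; if 90% was intended, it gives 82.5% and the one-sided claim would hold. Sidedness and the unusable alternative are separate faults, and the intended alternative is unknown.

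A reader might also infer that a two-sided test necessarily moves the critical count to 27. Section 11.2.1 names no two-sided method, and two common ones stay at 26. The equal-tailed choice is the one consistent with Table 1, but the plan does not prescribe it.

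None of this removes the conflict. Section 11.2.1 covers all tests without exception, and 18.6% is not an improvement on 70%.

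**Conclusion.** The point holds for the power sentence itself. It conflicts with section 11.2.1 on sidedness, its alternative is impossible as printed, and the power it states cannot be verified. On exact calculation, 80% power requires a true rate of full attendance of about 89.6% one-sided, or about 92.3% two-sided with equal tails. These two figures rest only on n = 30, the 70% null and the 5% level. The powers at 88.6% and 90% rest on assumed alternatives, and the move from 26 to 27 rests on the equal-tailed method.

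A reader might go further and conclude that 30 participants is unjustified or that the feasibility decision has two thresholds. Neither follows: the sample size was not derived from this test, and the decision rule in section 11.2.2 does not use it. This is a correction to the text, not to the design.

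**What to change.** Use one sidedness in sections 11.1 and 11.2.1, name the exact method, replace the 18.6% with the intended true rate, and restate the power. Any of these would do:

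- **One-sided.** Exempt the attendance test in 11.2.1, and state in 11.1: one-sided exact binomial test, reject at ≥26/30, actual size 3.0%, at least 80% power at a true rate of 89.6% or higher.
- **Two-sided.** Keep 11.2.1 as it is, and state in 11.1: equal-tailed exact binomial test, reject at ≥27/30 in the upper tail, at least 80% power at a true rate of 92.3% or higher.
- **No test.** Delete the power sentence and rely on the precision in Table 1, which is correct.

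If a test is kept, say that it is supportive and does not replace the criteria of section 11.2.2; otherwise a rejection count of 26 or 27 could be mistaken for a second success threshold beside 70% (21 of 30).

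The cost is a few sentences. No change to the sample size, endpoints or data collection is needed. The only downside is that the detectable rate becomes slightly less favourable.

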11.2 Statistical Analyses

11.2.1 General Approach

All data will be inspected for quality assurance prior to analysis. Data screening will focus on: (a) Missing data: we will determine the amount, the pattern, and randomness; (b) Outliers: we will identify observations that appear to be very high or very low and decide how to proceed based on the presumed cause; and (c) Inconsistencies: we will identify inconsistencies within a single variable and between variables. Initially, we will perform an exploratory data analysis and calculate descriptive statistics.

Transformations of the data in order to meet statistical assumptions will be undertaken when indicated. Type-1 error will be set to 5% ($\alpha = .05$) for calculating confidence intervals and performing hypothesis testing and all tests will be two-sided. If needed,

alphas will be adjusted accordingly for multiple comparisons using Bonferroni correction. Standard statistical goodness-of-fit measures will be used assessing any of the model fittings. Missing values will be handled with appropriate statistical methods. Last observation carried forward (LOCF) and multiple imputation will be considered for missing values.

Demographic and disease characteristic variables will be summarized using descriptive statistics. Counts and percentages will be used to summarize the distribution of categorical variables. Median, range, mean, and standard deviation will be used for continuous variables. Categorical variables will be tested using Fisher's exact test. Continuous variables will be tested using Student's t-test and/or Mann-Whitney U test. For correlation coefficients, Pearson's correlation coefficients and Spearman's correlation coefficients will be estimated along with corresponding 95% confidence interval. All statistical analyses will be carried out using SAS or SPSS, all of which are available to investigators through the University of Miami.

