11.2.3 Analysis of the Secondary Endpoint(s)

Preliminary Efficacy: The main outcomes will be health-related quality of life, general stress, and disease/dual-diagnosis related distress all of which will be continuous total scores. We will examine descriptive statistics (e.g., means, medians, standard deviations) among study variables. Based on the distribution of the data, we will select either paired t- tests or the Wilcoxon signed-rank test for paired samples to examine whether the following variables improve significantly following the intervention using total

scores and scores from subdomains. Linear regression will be used to examine study variables and the following change of endpoints between pre- and post-intervention:

- **The Functional Assessment of Cancer Therapy Scale-General:** This instrument will be used to assess HRQOL. This 5-point Likert scale instrument includes 27 items and yields four subscales (physical, social, emotional, and functional well-being) and a total score, with higher scores indicating better HRQOL (Cronbach's α from .85 to .92)²⁷.
- **The Medical Outcomes Study HIV Survey:** This is a widely accepted instrument to assess HRQOL in individuals living with HIV. The instrument includes 35 items that assess the ten dimensions of health, including mental health, quality of life, health distress, cognitive function, energy/fatigue, overall health, role function, physical function, pain, and social function. The subscales are scored as summated rating scales on a 0–100 scale where higher scores indicate better health (all Cronbach's α > .75)¹⁹.
- **Perceived Stress Scale:** This instrument will be used to assess the degree to which participants appraise their lives as stressful. It consists of 14 items, with seven positive items and seven negative items rated on a 5-point Likert scale. Positive items will be reversed coded and all items will be summed to generate a total score, with higher scores indicating greater stress (Cronbach's α = .86)²⁵.
- **The Impact of Event Scale:** This instrument will be used to measure dual-diagnosis- related distress. This 5-point Likert scale instrument includes 22 items and it was developed to assess post-traumatic stress disorder symptom clusters associated to a life-threatening event. It yields 3 subscales (intrusion, avoidance, and hyperarousal) and a total score. Higher scores indicate greater distress (Cronbach's α from .79 to .97)²⁶.

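### Twenty total and subscale scores are to be tested for improvement, but the plan does not say when Bonferroni applies or over which tests; the family should be fixed in advance and tested with Holm

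*Combined protocol and SAP*

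**What the plan says.** Section 11.2.1 (General Approach) states "Type-1 error will be set to 5" per cent for intervals and tests, and "all tests will be two-sided". The next sentence, which opens with the condition 'If needed', says "alphas will be adjusted accordingly for multiple comparisons using Bonferroni correction". It does not say what would make adjustment necessary, which tests form the family, or how many there are.

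Section 11.2.3 (Analysis of the Secondary Endpoint(s)) first describes the main outcomes, for three constructs, as continuous total scores. It then plans paired t-tests or Wilcoxon signed-rank tests "to examine whether the following variables improve significantly following the intervention using total" "scores and scores from subdomains". The instruments follow. FACT-G "yields four subscales (physical, social, emotional, and functional well-being) and a total score". For MOS-HIV, "The instrument includes 35 items that assess the ten dimensions of health", each scored 0 to 100, and no total is described. The Perceived Stress Scale has one total. The Impact of Event Scale has three subscales and a total. Section 11.2.3 does not mention adjustment.

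The Protocol Summary calls the analyses primarily descriptive and also plans effect sizes. Section 11.0 states a directional secondary hypothesis: lower stress and distress, better quality of life.

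**The concern.** The condition attached to Bonferroni can be settled after the p-values are known, and so can the divisor: 3 (constructs), 4 (instruments), 20 or 21 (all scores). The same data could therefore be reported as several significant improvements or as none, with both reports consistent with the plan.

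At stake is how the secondary hypothesis is read. Section 11.2.2 says the pilot's results are meant to underpin later randomised trials. A subscale picked out because it crossed an unadjusted 5% line could mislead the choice of endpoint for such a trial, and an unplanned 20-fold correction could hide a moderate change. Separately, Bonferroni is not the best choice once a family has been fixed, because Holm's procedure controls the same familywise error rate and never rejects fewer hypotheses.

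**Working it through.** The documents give no power, effect size or familywise error figure for these scores, so there is no stated figure to reproduce.

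**Inputs from the documents**
- Two-sided alpha 0.05 (11.2.1).
- 30 participants (11.1).
- Retention target 85% (11.2.2): 0.85 × 30 = 25.5, taken as 26 pairs.
- Score count (11.2.3): FACT-G 4 + 1 = 5; MOS-HIV 10; Perceived Stress 1; Impact of Event 3 + 1 = 4. Total 5 + 10 + 1 + 4 = **20**, or 21 with a MOS-HIV total.

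**Assumptions not in the documents**
- A common correlation between change scores of 0 to 0.7.
- A standardised paired change d of 0.5, with 0.8 for contrast.
- Normally distributed changes.

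**Step 1. All 20 tested at 0.05, no true change**

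Independent scores:
- Any p<0.05: 1 − 0.95^20 = 0.642 (21 scores: 0.659).
- A false improvement only: 1 − 0.975^20 = 0.397.
- Expected number of false positives: 20 × 0.05 = 1.0, whatever the correlation.

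Correlated scores, by simulation of 20 equicorrelated paired t-tests:

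| Correlation | Any p<0.05 | False improvement |
|---|---|---|
| 0 | 64% | about 40% |
| 0.3 | about 55% | about 29% |
| 0.5 | about 43% | about 22% |
| 0.7 | about 30% | about 15% |

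Results for 26 and 30 pairs agree to within about one percentage point.

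**Step 2. All 20 corrected by Bonferroni**

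The per-test level is 0.05/20 = 0.0025. Power of a two-sided paired t-test is P(T > t(1 − α/2; n − 1)), where T is noncentral t with n − 1 degrees of freedom and noncentrality d√n. For d = 0.5, d√n is 2.74 (n = 30) or 2.55 (n = 26).

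| Change d | Pairs | α = 0.05 | α = 0.0025 |
|---|---|---|---|
| 0.5 | 30 | 75% | 31% |
| 0.5 | 26 | 69% | 24% |
| 0.8 | 30 | 99% | 84% |
| 0.8 | 26 | 98% | 75% |

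**Step 3. Four scores, one per instrument**

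Bonferroni uses 0.05/4 = 0.0125 for each score. Holm orders the four p-values, compares them in turn with 0.05/4, 0.05/3, 0.05/2 and 0.05, and stops at the first failure. Average power per score, with d = 0.5 on all four and correlation 0.5:

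| Pairs | Bonferroni over 4 | Holm over 4 |
|---|---|---|
| 30 | 54% | about 64% |
| 26 | 46% | about 55% |

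**Step 4. Any of the four totals significant under Bonferroni over 20**

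Under the same assumptions (d = 0.5, correlation 0.5), at least one of the four is significant in about 61% of trials with 30 pairs and 52% with 26.

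**The case against.** The strongest reply is that little rests on these tests. The analyses are described as primarily descriptive and efficacy as preliminary; the sample size rests on feasibility, and the scores do not enter the feasibility criteria in 11.2.2. Section 11.2.3 already names total scores as the main outcomes, which points to a family of three or four. Bonferroni is a valid method, and most of the power gain over a 20-fold correction comes from shrinking the family rather than from Holm.

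Much of this stands, and it limits the size of the point. It does not remove it. Section 11.2.3 extends testing for significant improvement to the subdomains, nothing ties the correction to the totals, and the four-score family is incomplete until a MOS-HIV score is named.

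A reader might also infer three stronger things that the documents do not support:
- *Chance alone would usually support the secondary hypothesis.* The hypothesis is directional, and the FACT-G and Impact of Event totals contain their own subscales, so independence is implausible. The chance of a false improvement is about 40% at most, and 15% at correlation 0.7.
- *A 20-fold correction would almost never leave a significant result.* Step 4 gives 61% or 52% for at least one of four totals.
- *The correction removes most of the power.* That depends on an effect size the documents do not give. It holds at a change of 0.5 but not at 0.8.

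**Conclusion.** The gap is real and modest. The plan commits to significance tests on 20 scores and leaves both the decision to correct and the divisor open. Without adjustment, the chance of at least one false positive is 30% to 64% over assumed correlations of 0.7 to 0, against a nominal 5%; for false improvements alone it is 15% to 40%. With full Bonferroni correction, per-score power at a change of 0.5 falls by more than half, while at 0.8 most of it remains. The count of 20 and the independent-score figures follow directly from the documents; the rest depends on the assumed correlations and effect sizes. The two extremes are not the only options, because the plan's own statement of its main outcomes supplies most of a small family. The point bears on the interpretation of the secondary efficacy aim and leaves the feasibility conclusion untouched.

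**What to change.** - In 11.2.1, delete the conditional and state the family. It should be one score per instrument: FACT-G total, Perceived Stress total, Impact of Event total, and one MOS-HIV score named before the data are examined.
- Replace Bonferroni with Holm across these four at two-sided 5%.
- In 11.2.3, confine significance testing of pre-post change to that family. Report every subscale as mean change with a 95% confidence interval, labelled exploratory.

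The cost is a few sentences of wording, with no effect on recruitment, data collection or participants. The downside is that subscale results carry no significance claim, which fits the descriptive purpose stated in the Protocol Summary.
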